--	--

	
Post-PD Follow-up Phase:
 
Subjects will be followed for progression, overall survival (OS), and use of subsequent anticancer agents until study closure.

Population:	Subjects who have treatment-naïve CLL or SLL with active disease requiring therapy
Centers:	Multiple, US vs. ex-US

Inclusion Criteria:
 
Refer to Section 4 for the complete and detailed list of inclusion/exclusion criteria.
	
Disease Related
 
 1. Diagnosis of CLL/SLL that meets IWCLL diagnostic criteria (Hallek 2008). 2. Active disease meeting at least 1 of the following IWCLL criteria (Hallek 2008) for requiring treatment: 
 • Evidence of progressive marrow failure as manifested by the development of, or worsening of, anemia and/or thrombocytopenia • Massive, progressive, or symptomatic splenomegaly • Massive nodes or progressive or symptomatic lymphadenopathy • Progressive lymphocytosis • Constitutional symptoms 3. Measurable nodal disease by computed tomography (CT). 
Laboratory
 
 4. Adequate hematologic function independent of transfusion and growth factor support for at least 7 days, (with the exception of pegylated G-CSF [pegfilgrastim] and darbopoeitin which require at least 14 days) prior to screening laboratory assessment defined as: 
 • Absolute neutrophil count (ANC) >750/μL (750 cells/mm³ or 0.75×10^9/L) • Platelet count >30,000 /μL (30,000 cells/mm³ or 30×10^9/L). • Hemoglobin >8.0 g/dL 5. Adequate hepatic and renal function defined as: 
 • Serum aspartate transaminase (AST) or alanine transaminase (ALT) $\leq 3.0 \times$ upper limit of normal (ULN) • Creatinine Clearance (CrCl) ≥ 60 mL/min (eg, as estimated by Cockcroft-Gault) • Bilirubin $\leq 1.5 \times$ ULN (unless bilirubin rise is due to Gilbert's syndrome or of non-hepatic origin) 6. Prothrombin time (PT)/International normal ratio (INR) <1.5 x ULN and PTT (activated partial thromboplastin time [aPTT]) <1.5 x ULN (unless abnormalities are unrelated to coagulopathy or bleeding disorder).

[figure not shown]
[figure not shown]

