3.3. Study Schema; Fixed Duration Cohort

¹ Administer 12 cycles of ibrutinib + venetoclax unless discontinue for PD or toxicity. Subjects who discontinue treatment for reasons other than confirmed PD should continue participating in ongoing response follow-up visits until confirmed PD

² Refer to [Sections 3.1.3](#) and [5.3.3](#) for details regarding FD cohort Reintroduction

4. **SUBJECT SELECTION**

4.1. **Inclusion Criteria**

Prior to enrollment, each potential subject must satisfy all of the following inclusion criteria.

Disease Related

1. Diagnosis of CLL/SLL that meets IWCLL diagnostic criteria (Hallek 2008).
2. Active disease meeting at least 1 of the following IWCLL criteria (Hallek 2008) for requiring treatment:
 - Evidence of progressive marrow failure as manifested by the development of, or worsening of, anemia and/or thrombocytopenia
 - Massive, progressive, or symptomatic splenomegaly
 - Massive nodes or progressive or symptomatic lymphadenopathy
 - Progressive lymphocytosis
 - Constitutional symptoms
3. Measurable nodal disease by computed tomography (CT).

Laboratory

4. Adequate hematologic function independent of transfusion and growth factor support for at least 7 days (with the exception of pegylated G-CSF [pegfilgrastim] and darbopoeitin which require at least 14 days) prior to screening laboratory assessment defined as:
 - Absolute neutrophil count (ANC) >750 cells/ μL (750 cells/ mm^3 or $0.75 \times 10^9/\text{L}$)
 - Platelet count $>30,000/\mu\text{L}$ (30,000 cells/ mm^3 or $30 \times 10^9/\text{L}$)
 - Hemoglobin >8.0 g/dL
5. Adequate hepatic and renal function defined as:
 - Serum aspartate transaminase (AST) or alanine transaminase (ALT) $\leq 3.0 \times$ upper limit of normal (ULN)
 - Creatinine Clearance (CrCl) ≥ 60 mL/min (eg, as estimated by Cockcroft-Gault)
 - Bilirubin $\leq 1.5 \times$ ULN (unless bilirubin rise is due to Gilbert's syndrome or of non-hepatic origin)
6. Prothrombin time (PT)/International normal ratio (INR) $<1.5 \times$ (upper limit of normal) ULN and PTT (activated partial thromboplastin time [aPTT]) $<1.5 \times$ ULN (unless abnormalities are unrelated to coagulopathy or bleeding disorder).

Demographic

7. Men and women ≥ 18 and ≤ 70 years of age.
8. Eastern Cooperative Oncology Group (ECOG) performance status of 0-2.

Ethical/Other

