11.1.3. Severity Criteria (Grade 1-5)

Definitions found in the Hematologic Adverse Event Grading Scheme ([Hallek 2008](#)) will be used for grading the severity of hematologic AEs. Refer to [Appendix L](#) for the grading of hematologic AEs.

Definitions found in the Common Terminology Criteria for Adverse Events version 4.03 (CTCAE v4.03) will be used for grading the severity (intensity) of nonhematologic AEs. The CTCAE v4.03 displays Grades 1 through 5 with unique clinical descriptions of severity for each referenced AE. Should a subject experience any AE not listed in the CTCAE v4.03, the following grading system should be used to assess severity:

- Grade 1 (Mild AE) – experiences which are usually transient, requiring no special treatment, and not interfering with the subject’s daily activities
- Grade 2 (Moderate AE) – experiences which introduce some level of inconvenience or concern to the subject, and which may interfere with daily activities, but are usually ameliorated by simple therapeutic measures
- Grade 3 (Severe AE) – experiences which are unacceptable or intolerable, significantly interrupt the subject’s usual daily activity, and require systemic drug therapy or other treatment
- Grade 4 (Life-threatening or disabling AE) – experiences which cause the subject to be in imminent danger of death
- Grade 5 (Death related to AE) – experiences which result in subject death

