Appendix L. Hematologic Adverse Event Grading Scheme (Hallek 2008)

An evaluation of the hematologic toxicity in patients with advanced CLL/SLL must consider the high frequency of marrow involvement and previous exposure to chemotherapy with consequent medullary compromise at the initiation of therapy. The standard hematologic grading system for solid tumors cannot, therefore, be directly applied. A substantial proportion of patients would be considered to have Grade 2 to 4 hematologic toxicity before any therapy is given. Therefore, the following modified schema will be used to quantitate hematologic deterioration in patients with CLL/SLL.

Hematologic Grading Scheme

Decrease in Platelets or Hgb (Nadir) from Pre-treatment Value, %	ANC/ μ L (nadir) ^c	Toxicity Grade
0 - 10% ^a	≥ 2000	0
11 - 24% ^{a,b}	≥ 1500 and < 2000	1
25 - 49% ^{a,b}	≥ 1000 and < 1500	2
50 - 74% ^{a,b}	≥ 500 and < 1000	3
$> 75%$ ^{a,b}	< 500	4

- Platelet counts must be below normal levels to be Grades 1 to 4. If at any level of decrease, the platelet count falls below $20 \times 10^9/L$, toxicity will be considered Grade 4. If the baseline platelet count is $< 20 \times 10^9/L$, platelet toxicity cannot be evaluated.
- Hemoglobin levels must be below normal levels to be Grades 1 to 4. Baseline and subsequent Hgb values must be determined the day of any given transfusion.
- If the ANC was $< 1000/\mu L$ before therapy, the patient is not evaluable for toxicity referable to the ANC.

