## 5. SAFETY ASSESSMENTS

Safety data will be summarized for the all treated population. Table 3 summarizes the safety analyses to be performed.

Adverse events will be coded in accordance with the MedDRA. Severity of AEs will be graded by the investigator according to the NCI-CTCAE v4.03 for non-hematological AEs and IWCLL 2008 guidelines for hematologic toxicity.

Treatment emergent period is defined as the period from the date of the first dose of study treatment up to 30 days after the date of the last dose of study treatment or the day before initiation of subsequent antineoplastic therapy or reintroduction of study treatment, whichever comes first.

The treatment emergent adverse events (TEAE) are those events that occur or worsen during the treatment-emergent period or that are related to the study treatment. Unless otherwise specified, only TEAEs will be included in the adverse event summaries. For MRD cohort, TEAEs within first 16 cycles (pre-randomization phase) and overall treatment emergent period (pre-randomization and randomization phase) will be both summarized.

All laboratory values will be converted to and reported in international system of units (SI). Hematologic parameters including platelet counts, hemoglobin, and neutrophils will be assessed by the grading scale for hematologic toxicity in CLL studies in the IWCLL 2008 guidelines. All other gradable laboratory parameters will be graded using the NCI CTCAE v4.03. Unless otherwise specified, only baseline and post-baseline values collected during the treatment-emergent period will be included in the safety analysis.

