**Table 3: Summary of Safety Assessments**

Assessment Type	Definition	Analysis Methods
AE	TEAEs, SAEs, Grade 3 or worse TEAEs, related TEAEs, TEAEs leading to treatment discontinuation, TEAEs leading to dose reduction, TEAEs leading to death, protocol- defined events of special interest and other safety observations.	Descriptive summary statistics and/or listings
Lab	Worst post-baseline toxicity grade for selected gradable hematology and chemistry. Abnormalities in creatinine clearance, uric acid, and liver function.	Descriptive summary statistics and/or listings
Vital Signs	Blood pressure, heart rate	Descriptive summary statistics and/or listings

TEAE= treatment emergent adverse event; SAE= serious adverse event.

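### Subjects can enter with ANC 751-999/µL, but the grading scale calls them not evaluable for neutrophil toxicity, so a new fall below 500/µL may have no Grade 4 entry

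*Protocol*

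**What the plan says.** Entry: the Protocol Synopsis gives the limit as "Absolute neutrophil count (ANC) >750"/µL, and Protocol Section 4.1, criterion 4, repeats it: "Absolute neutrophil count (ANC) >750 cells"/µL.

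Scale: Protocol Section 11.1.3 says the Appendix L scheme "will be used for grading the severity of hematologic AEs". SAP Section 5 has investigators grade adverse events by CTCAE v4.03 if non-hematologic, "and IWCLL 2008 guidelines for hematologic toxicity". For laboratory data, SAP Section 5 states: "Hematologic parameters including platelet counts, hemoglobin, and neutrophils will be assessed by the grading scale for hematologic toxicity in CLL studies". Protocol Section 10.4.11 says the same.

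Evaluability: footnote c of Appendix L provides that, if the ANC was under 1000/µL "before therapy, the patient is not evaluable for toxicity referable to the ANC".

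Output: SAP Table 3 lists "Worst post-baseline toxicity grade for selected gradable hematology and chemistry" and "Grade 3 or worse TEAEs". SAP Section 5 bases safety summaries on the all treated population. Neither document gives a substitute grade, a denominator rule or a separate listing for subjects who are not evaluable.

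**The concern.** The entry limit and the evaluability limit overlap. A subject admitted with a count in the overlap has no neutrophil grade to be assigned, however far the count later falls. These subjects start lowest, so their omission is not random.

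The toxicity is a prominent one. Protocol Section 1.3.2.2 puts neutropenia first among Grade 3 or higher events with venetoclax monotherapy in CLL/SLL (36.8%). Section 1.3.3.2 gives Grade 3 or 4 neutropenia in 41% (98/240) of previously treated 17p-deletion patients. Those populations differ from this one, so the figures show relevance and are not expected rates here.

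At stake is the accuracy of the reported Grade 4 neutropenia rate in both cohorts.

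**Working it through.** The plan states no figure on this point, so there is none to reproduce. The check is a comparison of limits, followed by an illustration of size.

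**Step 1. Overlap.** Eligible: ANC >750/µL (Section 4.1). Not evaluable: pre-therapy ANC <1000/µL (Appendix L, footnote c). Both hold for whole-number counts of 751-999/µL.

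**Step 2. Are the other parameters affected?** Platelets are not evaluable only below 20 × 10⁹/L at baseline, while entry requires more than 30 × 10⁹/L, so there is no overlap. Appendix L sets no baseline floor for hemoglobin. The gap concerns neutrophils only.

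**Step 3. What is lost?** The ANC column of Appendix L uses absolute nadirs: Grade 3 is ≥500 and <1000/µL, and Grade 4 is <500/µL. A baseline of 751-999/µL already lies in the Grade 3 band, so remaining there is not new toxicity. The informative loss is a fall below 500/µL.

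**Step 4. Which tables?** The worst post-baseline laboratory grade is derived from the scale, so footnote c applies directly. For adverse events the result is uncertain: Protocol Sections 11.4.1 and 11.4.2 require a severity for every event, while the scale named for that severity declines to give one.

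**Step 5. Size.** Let N = 150 + 125 = 275 planned subjects, f = share with baseline ANC <1000/µL, and g = share of those who fall below 500/µL. The documents give neither f nor g; both are assumed.

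- Missed Grade 4 cases = N × f × g.
- If these subjects stay in the denominator as non-events, the rate is understated by f × g.
- If they are removed, and r is the Grade 4 rate in the remaining subjects, the true rate is (1 − f) × r + f × g and the reported rate is r. The understatement is f × (g − r), which is smaller than f × g and is zero when g = r.

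With g = 0.5 and subjects kept in the denominator:

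| f | Not evaluable (275 × f) | Missed Grade 4 (× 0.5) | Understatement (f × 0.5) |
|---|---|---|---|
| 2% | 5.5 | 2.8 | 1.0 point |
| 5% | 13.8 | 6.9 | 2.5 points |
| 10% | 27.5 | 13.8 | 5.0 points |

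At the extremes, g = 0 gives no loss and g = 1 gives 2, 5 and 10 points.

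**Step 6. Which value decides?** Eligibility rests on the screening count. Protocol Section 10.4.11 defines baseline as the last value on or before first dose. The two can differ, so the affected set should be identified by baseline ANC <1000/µL.

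**The case against.** Footnote c is part of a cited disease-specific scale, and Appendix L explains its purpose: many patients with marrow involvement would otherwise count as toxic before any treatment. Grading everyone by absolute cut-offs would score a subject stable at 800/µL as post-baseline Grade 3 with no deterioration. This stands. It argues against replacing the IWCLL grading, but it does not tell the programmer what to do with subjects the scale cannot grade.

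Three stronger readings are tempting, and the documents do not support them.

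- A reader might infer that severe neutropenia in these subjects disappears from the safety report. It does not. Any-grade TEAEs, SAEs, and TEAEs leading to dose reduction or discontinuation need no grade. No section says that an adverse event goes ungraded or is removed because of the baseline ANC.
- A reader might infer that such a subject could not have had a neutropenia DLT, because Protocol Section 5.2.1 refers to Appendix L. That section writes the criterion out as an absolute count below 500 lasting more than 7 days, which such a subject can meet. SAP Section 1.5.1 also reports the run-in complete, with no DLT in 14 subjects.
- A reader might infer a known downward bias. Its size rests on assumed shares, and its direction depends on a denominator rule that the documents do not give.

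It is also fair to say that no efficacy endpoint, hypothesis test or sample size is involved, and that the dose-modification triggers in Protocol Sections 5.4.1.4 and 5.4.2.5 state absolute neutrophil counts.

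**Conclusion.** The point holds in a limited form. The eligibility and evaluability limits clash at 751-999/µL, both documents make Appendix L the operative scale, and neither says how the affected subjects are graded or counted. Following the stated rule leaves a new fall below 500/µL without a Grade 4 entry in the worst-grade laboratory table, and possibly without one in the Grade 3 or worse TEAE table.

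The under-count applies to Grade 4 and arises if these subjects remain in the all treated denominator. Under the assumptions shown it is 1 to 5 points. With few such subjects it would be negligible, and the documents do not allow a closer estimate. This is a modest reporting defect, worth correcting because the data are already collected.

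**What to change.** In SAP Section 5 and Table 3:

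1. Keep the IWCLL grading of neutrophils, but report it with its own evaluable N and state the number of subjects with baseline ANC <1000/µL.
2. Add, for all treated subjects in each cohort, a baseline-to-worst ANC shift table using the absolute cut-offs already in Appendix L.
3. In that table, count a subject with baseline ANC 500-999/µL as having treatment-emergent Grade 4 neutropenia only on a fall below 500/µL. An unchanged baseline Grade 3 value is not counted as new.

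The cost is a few lines of SAP text and one extra table from hematology already scheduled. The reported Grade 4 neutropenia rate may be slightly higher. No change to eligibility or dosing rules is involved.

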1.1.2. Current Treatment Options in Previously Untreated CLL

The results of clinical studies in previously untreated CLL have demonstrated major advances in therapy over the last decade. The most active regimen described thus far, on the basis of a single-center experience at the MD Anderson Cancer Center (Keating 2005) and subsequent randomized CLL8 trial (Hallek 2010), is the chemoimmunotherapeutic (CIT) combination of fludarabine, cyclophosphamide, and rituximab (FCR). FCR resulted in significant improvement in PFS and OS compared with fludarabine and cyclophosphamide alone, with a hazard ratio for progression of 0.51 (95% CI: 0.39, 0.67) for patients less than 70 years of age (N = 736) (Hallek 2010, Casak 2011). Although numerous subsequent attempts have been made to improve on FCR eg, through the addition of mitoxantrone, alemtuzumab or granulocyte macrophage colony-stimulating factor (Parikh 2011, Bosch 2009, Reynolds 2012), increasing the dose of rituximab (FCR3) (O'Brien 2005), substituting cladribine or pentostatin for fludarabine (Wierda 2012, Bryan 2011), or combining rituximab with bendamustine (Fischer 2012) so far FCR remains the most active regimen and regarded as a standard of care for young fit first line patients (Hillmen 2010).

Despite the improved efficacy of CIT, only 40-45% of patients treated with these approaches currently achieve a complete response (CR) and many patients (including those achieving CR) eventually relapse (Hallek 2010, Tam 2008, Kay 2007, Fischer 2016). In some patients, CIT has resulted in attainment of undetectable minimal residual disease (MRD), defined as detection of <1 CLL cell in 10,000 normal leukocytes by either polymerase chain reaction assay or 4 color flow cytometry. These MRD-negative remissions are associated with longer PFS and OS (Bottcher 2012, Strati 2014), however, only 43-49% of patients who are evaluated for MRD (27-43% of ITT patients) are able to achieve MRD-negative remissions (Bottcher 2012, Strati 2014). Additionally, MRD-negative remissions are achieved in a lower percent of unmutated vs mutated IGHV patients post CIT (33% vs 50.7% respectively of those evaluated) (Thompson 2016). Although some patients derive significant benefit from CIT, fludarabine based CIT regimens result in substantial toxicity including profound immunosuppression, prolonged cytopenias (which can restrict salvage therapy options at the time of recurrence), and a 5-10% risk of therapy-related myelodysplasia (MDS) (Tam 2008, Keating 2005, Ferrajoli 2005). These toxicities are problematic since most CLL patients are >age 50 at diagnosis and many patients have comorbidities that limit their ability to receive CIT (Hallek 2013). Even among younger fit CLL patients, >25% are unable to tolerate FCR-based CIT. Phase 3 trial indicate that 56% of patients experience Grade 3-4 myelosuppression, 25% infectious complication, 47% require dose reductions, and >25% of patients are unable to complete the intended 6 cycles of FCR induction even with dose reductions (Hallek). While FCR has been a major advance in the CLL treatment, it is associated with significant toxicity that limits the benefit of this approach for many patients.

Recently, in the RESONATE-2 randomized trial, single-agent ibrutinib (administered daily until progression or unacceptable toxicity) demonstrated superior PFS and OS compared to chlorambucil in previously untreated CLL patients (Burger 2015). At 18.4 months of follow up,

ibrutinib significantly reduced the risk of progression or death by 84% compared to chlorambucil (median PFS not reached vs. 18.9 months respectively; hazard ratio, 0.16; $P < 0.001$). Notably, the 18-month PFS was 89% in both unmutated and mutated IGHV subgroups treated with ibrutinib, compared to 47% and 51% in these respective subgroups treated with chlorambucil. Additionally, ibrutinib reduced the relative risk of death by 84% (hazard ratio, 0.16; $P = 0.001$). The overall response rate was higher with ibrutinib compared with chlorambucil (86% vs. 35%, $P < 0.001$), and the rates of sustained increases from baseline values in the hemoglobin and platelet levels were higher with ibrutinib. Adverse events of any grade that occurred in at least 20% of the patients receiving ibrutinib included diarrhea, fatigue, cough, and nausea, and were mainly Grade 1-2. At 18.4 months of follow-up, 87% of the patients in the ibrutinib group continued on therapy (Burger 2015). Ibrutinib was approved by US FDA in March 2016 based on these data for the first line treatment of CLL.

Although ibrutinib has resulted in an improvement in PFS and OS in treatment-naïve patients (Burger 2015), and previously treated patients (Byrd 2014), single-agent ibrutinib has rarely demonstrated the ability to induce undetectable MRD by PCR or 4 color flow cytometry with a sensitivity of $< 1 \times 10^{-4}$. The addition of ibrutinib to bendamustine + rituximab (BR) resulted in a higher MRD-negative CR/CRi rate in previously treated CLL patients compared to placebo + BR (4.2% vs 1.5% by IRC; 9.3% vs 2.4% by investigator assessment) (Chanan-Khan 2016). The MRD-negative rate reached a plateau 9 months after completion of placebo + BR, however increased overtime with continued ibrutinib therapy (Fraser 2016).

Phase 1 data of single-agent venetoclax in relapsed CLL or SLL patients ($n=56$ in the dose escalation cohort and $n=60$ in the expansion cohort) demonstrated reduction of CLL burden in the blood, lymph nodes and bone marrow, with a pooled overall response rate (ORR) of 79% including 20% CR/CRi (Roberts 2015). The response rate did not differ by risk factors, including deletion 17p CLL, resistance to fludarabine, unmutated IGHV, or bulky disease. Importantly, 35% (6/17) of those patients who achieved CR and were evaluated for MRD in bone marrow became MRD-negative. In the dose-escalation cohort, tumor lysis syndrome (TLS) occurred in 10 of 56 patients (18%), including clinical TLS in 3 patients and laboratory TLS in 7 patients. In the expansion cohort, patients received an extended step-wise dose ramp-up schedule with TLS prophylaxis and hospitalization according to their level of TLS risk, resulting in no cases of clinical TLS and reduced laboratory TLS. Adverse event of any grade that occurred in at least 20% of patients included diarrhea, upper respiratory tract infection, nausea, neutropenia, fatigue, cough, pyrexia, anemia, headache, constipation, and thrombocytopenia. Phase 2 data of single-agent venetoclax in ultra high-risk relapsed/refractory del17p CLL ($N=107$) demonstrated a 79% ORR including 7.5% CR/CRi (Stilgenbauer 2015). No detectable MRD was observed in peripheral blood in 21% of responders with MRD assessments (17% of whole cohort). Venetoclax received accelerated approval from US FDA in April 2016 based on this data for patients with CLL with 17p deletion who have received at least one prior therapy. Venetoclax received conditional approval from the European Commissions in December 2016 for the treatment of patients with CLL in the presence of 17p deletion or *TP53* mutation in adult patient who are unsuitable or have failed a B-cell receptor pathway inhibitor, as well as for the treatment

of CLL in the absence of 17p deletion or TP53 mutation in adult patients who have failed both chemo-immunotherapy and a B-cell receptor pathway inhibitor. Venetoclax, both as a single agent and in combination with other therapeutic agents, continues to show promising efficacy in oncology subject populations. The ORR in subjects with CLL/SLL was 74% (IRC-assessed) and 74% (investigator-assessed) for single-agent venetoclax (Study M12-175 and Study M13-982, respectively), ranged from 67% to 57% for subjects with ibrutinib- or idelalisib-resistant CLL in Study M14-032, and was 86% for venetoclax administered in combination with rituximab (Study M13-365).

